4.6.	Follow-Up Questionnaire	
Subjects will respond to the following questionnaires:
 
1. CLUE Follow-up

Visit 4: Treatment 2 Follow-Up			
Step	Procedure	Details	
		2. GSI Product Performance	
4.7.	Visual Acuity	Record the distance Snellen visual acuity with the contact lenses (OD, OS, and OU) to the nearest letter. Subjects must read the smallest line until at least 50% of the letters are read incorrectly.	
4.8.	logMAR (ETDRS) Visual Acuity	
Perform 4 m distance ETDRS logMAR visual acuity test OD and OS under the following conditions:
 
 • Bright illumination (e.g., >400 lux), with high contrast charts (HLHC); • The right eye will read Chart 1 • The left eye will read Chart 2 	
4.9.	Subjective Lens Fit Assessment	
Subjective Assessment of the Lens Fit. If the fit is graded as unacceptable based on the criteria below, then the subject is discontinued from the study and will not be replaced.
 
 1. Limbal exposure in any gaze 2. Edge lift 3. Insufficient and/or excessive movement in all three movement categories 	
4.10.	Surface Deposits	Record any front and back surface lens deposits.	
4.11.	Lens Removal & Storage	Both lenses will be removed and stored wet in a labeled container with Opti-Free® PureMoist®. The lenses can be stored refrigerated or frozen prior to shipment back to the Sponsor. Lenses will be stored at JJVCI for 45 days after LSLV for laboratory testing (Section 7.4).	
4.12.	Slit Lamp Findings	Slit Lamp Classification Scale [REDACTED] will be used to grade the findings. Record only whole numbers. Limbal and Bulbar Conjunctival Hyperemia findings [REDACTED] and Corneal Staining Assessment [REDACTED] will be emphasized using a more detailed scale.	[REDACTED] [REDACTED] [REDACTED]

Visit 4: Treatment 2 Follow-Up		
Step	Procedure	Details
		
Note: Findings must be grade 2 or less as graded on the FDA scale [REDACTED] to continue onto Trial Period 2. If the subject is not eligible, they must be followed as an adverse event. Once resolved, the subject is terminated from the study. Adverse events must be reported to the JJVC monitors immediately.

4.13.	Eye Rinse	
The study coordinator, investigator, or technician will rinse the subject's eyes thoroughly with saline.

Visit 4: Treatment 3 Lens Fitting		
Step	Procedure	Details
4.14.	Lens Selection	
Assign the study lens based on the randomization scheme.
 
Select the contact lens power based on subjective best sphere refraction.
 
Record the test condition.

4.15.	Lens Insertion	
The Investigator or the subject inserts the study lenses. Record the time of lens insertion.
 
Check for lens damage under the slit lamp before proceeding with lens settling.
 
Replace damaged lenses if applicable.

4.16.	Lens Settling	Allow the study lenses to settle for a minimum of 5 minutes.
4.17.	Subjective Best Sphere Over Refraction	
Perform a spherical over-refraction OD and OS. Optimize the lens power to achieve an over-refraction of ± 0.00 D OD and OS.
 
Ensure that any new lenses are not damaged.
 
One modification attempt will be allowed.

4.18.	Time Interval	Please wait for at least 10 minutes from final lens insertion to continue.
4.19.	Subject Reported Ocular Symptoms	Subjects will respond to a verbal open-ended symptoms questionnaire.

Visit 4: Treatment 3 Lens Fitting		
Step	Procedure	Details
4.20.	Visual Acuity	
Record the distance Snellen visual acuity with the contact lenses (OD, OS, and OU) to the nearest letter. Smaller lines must be shown until the subject incorrectly identifies at least 50% of the letters.

4.21.	Distance ETDRS logMAR Visual Acuity	
Perform 4 m distance ETDRS logMAR visual acuity test OD and OS under the following conditions:
 
 • Bright illumination (e.g., >400 lux), with high contrast charts (HLHC); • The right eye will read Chart 3 • The left eye will read Chart 4
4.22.	Subjective Lens Fit Assessment	
Subjective Assessment of the Lens Fit. If the fit is graded as unacceptable based on the criteria below, then the subject is discontinued from the study and will not be replaced.
 
 1. Limbal exposure in any gaze 2. Edge lift 3. Insufficient and/or excessive movement in all three movement categories
4.23.	Continuance	
For the subject to continue in the study, they must meet all three of the following criteria:
 
 1. Visual acuity is 20/30 or better OD and OS 2. The lens fit is acceptable OD and OS 3. Investigator approval. If the Investigator does not approve the dispensing of the first study lens, then the study is terminated for that subject.
4.24.	Dispense	
The lenses will be dispensed for 13-15 days.
 
 1. The subjects should wear their lenses similar to the inclusion criteria: ≥ 6 hours per day, ≥ 5 days per week. 2. The lenses will be worn as daily wear only. 3. All subjects will be provided Opti-Free® PureMoist® to be used in a rub regime. 4. Preservative-free rewetting drops are permitted if needed.

Visit 4: Treatment 3 Lens Fitting		
Step	Procedure	Details
		
5. The lenses must be stored in the supplied case out of direct sunlight.
 
Note 1: In the event a lens is lost or damaged, the subject will return to the investigator site for replacement (extra lenses cannot be given at the dispensing visit).
 
Note 2: The subject's habitual contact lenses cannot be worn at any time during the study.

VISIT 5

The follow-up will occur 13-15 days after the dispensing of the third study lenses. The subjects must enter the visit wearing their study contact lenses.

Visit 5: Treatment 2 Follow-Up		
Step	Procedure	Details
5.1.	Adverse Events and Concomitant Medications Review	
Review the subject's concomitant medications and record any changes from the previous study visit.
 
Record any adverse events or medical history changes from the previous study visit.

5.2.	Wearing Time	Record the average wearing time and comfortable wearing time.
5.3.	Compliance	Confirm compliance with the prescribed wear schedule. Outdoor and total hours will be asked.
5.4.	Subject Reported Ocular Symptoms	Subjects will respond to a verbal open-ended symptoms questionnaire.
5.5.	Follow-Up Questionnaire	
Subjects will respond to the following questionnaires:
 
 1. CLUE Follow-up 2. GSI Product Performance
5.6.	Visual Acuity	Record the distance Snellen visual acuity with the contact lenses (OD, OS, and OU) to the nearest letter. Subjects must read the smallest line until at least 50% of the letters are read incorrectly.

Visit 5: Treatment 2 Follow-Up		
Step	Procedure	Details
5.7.	logMAR (ETDRS) Visual Acuity	
Perform 4 m distance ETDRS logMAR visual acuity test OD and OS under the following conditions:
 
 • Bright illumination (e.g., >400 lux), with high contrast charts (HLHC); • The right eye will read Chart 1 • The left eye will read Chart 2
5.8.	Subjective Lens Fit Assessment	
Subjective Assessment of the Lens Fit. If the fit is graded as unacceptable based on the criteria below, then the subject is discontinued from the study and will not be replaced.
 
 1. Limbal exposure in any gaze 2. Edge lift 3. Insufficient and/or excessive movement in all three movement categories
5.9.	Surface Deposits	Record any front and back surface lens deposits.
5.10.	Lens Removal & Storage	Both lenses will be removed and stored wet in a labeled container with Opti-Free® PureMoist®. The lenses can be stored refrigerated or frozen prior to shipment back to the Sponsor. Lenses will be stored at JJVCI for 45 days after LSLV for laboratory testing (Section 7.4).
5.11.	Slit Lamp Findings	
Slit Lamp Classification Scale [REDACTED] will be used to grade the findings. Record only whole numbers. Limbal and Bulbar Conjunctival Hyperemia findings [REDACTED] and Corneal Staining Assessment [REDACTED] will be emphasized using a more detailed scale.
 
Note: Findings must be Grade 2 or less as graded on the FDA scale [REDACTED] Otherwise they must be followed as an adverse event. Adverse events must be reported to the JJVC monitors immediately.

Visit 5: Treatment 2 Follow-Up			
Step	Procedure	Details	
5.12.	Eye Rinse	The study coordinator, investigator, or technician will rinse the subject's eyes thoroughly with saline.	

FINAL EVALUATION

The final evaluation will ordinarily take place immediately following the last scheduled follow-up visit per the study protocol. It may also take place at any point the subject discontinues the study or is terminated from the study.

Final Evaluation			
Step	Procedure	Details	
F.1	Final Exam Form	Indicate if the subject completed the study successfully. If subject discontinued from the study indicate the reason.	
F.2	Best-corrected Distance Visual Acuity	Record the subject's best corrected distance visual acuity with refraction OD, OS, and OU.	

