3.3. Exclusion Criteria

Potential subjects who meet any of the following criteria will be excluded from participating in the study:

1. Currently pregnant or lactating (subjects who become pregnant during the study will be discontinued).
2. Any systemic disease, autoimmune disease, or use of medication, which may interfere with contact lens wear. This may include, but not be limited to, diabetes, hyperthyroidism, recurrent herpes simplex/zoster, Sjögren's syndrome, xerophthalmia, acne rosacea, Stevens-Johnson syndrome, and immunosuppressive diseases or any infectious diseases (e.g. hepatitis, tuberculosis).
3. Use of any of the following medications within 1 week prior to enrollment: oral retinoid isotretinoin (e.g. Accutane), oral tetracyclines, topical scopolamine, oral (e.g. Seldane, Chlor-Trimeton, and Benadryl) and ophthalmic antihistamines, oral phenothiazines (e.g., Haldol, Mellaril, Thorazine, Elavil, Pamelor, Compazine), oral and ophthalmic Beta-adrenergic blockers (e.g., Propranolol, Timolol, and Practolol), systemic steroids, and any prescribed or over the counter (OTC) ocular medication.
4. Entropion, ectropion, extrusions, chalazia, recurrent styes, glaucoma, history of recurrent corneal erosions, aphakia, or moderate or above corneal distortion.

5. Any previous, or planned, ocular or interocular surgery (e.g., radial keratotomy, PRK, LASIK, etc.).
6. Any Grade 3 or greater slit lamp findings (e.g., edema, corneal neovascularization, corneal staining, tarsal abnormalities, conjunctival injection) on the FDA classification scale, any previous history or signs of a contact lens-related corneal inflammatory event (e.g., past peripheral ulcer or round peripheral scar), or any other ocular abnormality that may contraindicate contact lens wear.
7. Any known hypersensitivity or allergic reaction to Optifree®PureMoist® multi-purpose care solution or Eye-Cept® rewetting drop solution
8. Any ocular infection, allergy or clinically significant ocular disease (e.g. corneal edema, uveitis, severe keratoconjunctivitis sicca, ocular hypertension), or ocular conditions (e.g. strabismus), which might interfere with the study.
9. Any corneal distortion resulting from previous hard or rigid gas permeable contact lens wear.
10. Toric, extended wear, monovision or multi-focal contact lens correction.
11. Participation in any contact lens or lens care product clinical trial within 30 days prior to study enrollment.

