2.5.	Preference	Subjects will respond to a preference questionnaire comparing study lens 1 to their habitual lenses.

Visit 2: Treatment 1 Follow-Up 1		
Step	Procedure	Details
2.6.	Follow-Up Questionnaire	Subjects will respond to the following questionnaires: 1. CLUE Follow-up 2. GSI Product Performance
2.7.	Entrance Visual Acuity	Record the distance Snellen visual acuity with the contact lenses (OD, OS, and OU) to the nearest letter. Subjects must read the smallest line until at least 50% of the letters are read incorrectly.
2.8.	Subjective Lens Fit Assessment	Subjective Assessment of the Lens Fit. If the fit is graded as unacceptable based on the criteria below, then the subject is discontinued from the study and will not be replaced. 1. Limbal exposure in any gaze 2. Edge lift 3. Insufficient and/or excessive movement in all three movement categories
2.9.	Surface Deposits	Record any front and back surface lens deposits.
2.10.	Temporary Lens Removal & Storage	Both lenses will be removed and temporarily stored in a lens case with either saline or Opti-free® Puremoist®. The lenses will be reinserted in step 2.13.
2.11.	Slit Lamp Findings	Slit Lamp Classification Scale [REDACTED] will be used to grade the findings. Record only whole numbers. Limbal and Bulbar Conjunctival Hyperemia findings [REDACTED] and Corneal Staining Assessment [REDACTED] will be emphasized using a more detailed scale. Note: Findings must be Grade 2 or less as graded on the FDA scale [REDACTED] to continue onto Trial Period 2. If the subject is not eligible, they must be followed as an adverse event. Once resolved, the subject is terminated from the study. Adverse events must be reported to the JJVC monitors

Visit 2: Treatment 1 Follow-Up 1		
Step	Procedure	Details
		immediately.
2.12.	Eye Rinse	The study coordinator, investigator, or technician will rinse the subject's eyes thoroughly with saline.
2.13.	Lens Reinsertion	The lenses removed in step 2.10 will be reinserted. The subject will wear the same lenses an additional 6-8 days to their next scheduled visit.
2.14.	Exit Visual Acuity	Record the distance Snellen visual acuity with the contact lenses (OD, OS, and OU) to the nearest letter. Subjects must read the smallest line until at least 50% of the letters are read incorrectly.

VISIT 3

The follow-up will occur 6-8 days following Visit 2. The subjects must enter the visit wearing their study contact lenses.

Visit 3: Treatment 1 Follow-Up 2		
Step	Procedure	Details

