8.2. Withdrawal/Discontinuation from the Study

A subject will be withdrawn from the study for any of the following reasons:

- Subject death during the study period
- Subject withdrawal of consent
- Subject not compliant to protocol (e.g. Subject more than 2 days out of visit window).
- Subject lost to follow-up
- Subject no longer meets eligibility criteria (e.g. the subject becomes pregnant)

- Subject develops significant or serious adverse events causing discontinuation of study lens wear (subjects missing more than 2 days of missed lens wear within a period 1 of week should be discontinued)
- Subjects who have experienced a Corneal infiltrative Event (CIE)
- Investigator's clinical judgment regarding the subject safety reasons (that it is in the best interest of the subject to stop treatment)
- Subject missed any scheduled study visits
- Subject not compliant with study lens wear schedule
- Subject not successfully dispensed due to lack of efficacy and safety including poor vision, poor comfort or unacceptable fit

For discontinued subjects, the Investigator will:

- Complete the current visit (scheduled or unscheduled)
- Complete the Final Evaluation, indicating the reason that the subject was discontinued from the study
- Record the spherocylindrical refraction with best corrected distance visual acuity
- Collect used test article(s) (worn or brought to the visit) from the subject and discard them, unless otherwise stated in Section 0
- Collect all unused test article(s) from the subject

Investigator will discuss with sponsor before enrolling any additional subjects if a subject discontinues from the study prematurely.

In cases where a subject is lost to follow-up, every possible effort must be made to contact the subject and determine the reason for discontinuation/withdrawal. The measures taken to follow up must be documented including two written attempts and a certified letter (or equivalent) as the final attempt.

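### The Visit 2 table orders lens reinsertion and 6-8 more days of wear whatever the slit lamp grade; its Grade 2 limit governs only entry to Period 2.

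*Combined protocol and SAP*

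**What the plan says.** All of the Visit 2 text is in the step table of protocol section 7.2.

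- Step 2.10 removes both lenses for the slit lamp examination and already commits to the outcome: "The lenses will be reinserted in step 2.13".
- Step 2.11 grades the eye. Its note requires Grade 2 or less on the FDA scale "to continue onto Trial Period 2. If the subject is not eligible, they must be followed as an adverse event". It then says "Once resolved, the subject is terminated from the study", and it closes by requiring that adverse events be reported to the sponsor's monitors at once.
- Step 2.13 says "The lenses removed in step 2.10 will be reinserted", and adds "The subject will wear the same lenses an additional 6-8 days to their next scheduled visit".
- Step 2.14 measures exit acuity with the lenses on the eye.

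Elsewhere, section 3.3 (criterion 6) excludes "Any Grade 3 or greater slit lamp findings". The withdrawal grounds in section 8.2 include "Subject no longer meets eligibility criteria (e.g. the subject becomes pregnant" and "Subject develops significant or serious adverse events causing discontinuation of study lens wear", as well as corneal infiltrative events and the investigator's safety judgment. Section 13.1 lists Grade 3 or higher corneal findings among the significant adverse events, a class that warrants temporary or permanent discontinuation of the test article.

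**The concern.** The grade is obtained between steps 2.10 and 2.13, yet neither step uses it. The one grade rule in the table is attached to the wrong event. Period 2 begins with the Treatment 2 fitting at Visit 3, so a limit on entering Period 2 does not decide whether the same lens goes back in at Visit 2.

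A site working down the table meets an explicit order to reinsert and no explicit order to stop wear. It has to infer the stop from sections 3.3, 8.2 and 13.1. What is at stake is the protection of the individual subject: a lens placed back on an eye that has just shown a Grade 3 or higher finding, for up to 6-8 days if nothing else intervenes.

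**Working it through.** **1. The same note at four visits**

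| Step | What the note governs | What comes next | Does it work as a gate? |
|---|---|---|---|
| 2.11 | Entry to Period 2 | Reinsertion (2.13) and 6-8 more days of Period 1 | No: the gated event is a visit away |
| 3.12 | Entry to Period 2 | Period 2 lens fitting | Yes |
| 4.12 | Entry to Period 2 | Period 3 lens fitting | Yes in effect; the label is wrong |
| 5.11 | Adverse event follow-up only | End of study | Adapted to its visit |

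The wording fits Visit 3. Its use at Visits 2 and 4 looks like text carried over without adjustment. Within Visit 2 itself, step 2.8 shows what an immediate stop looks like: an unacceptable fit discontinues the subject.

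**2. How far the rest of the protocol closes the gap**

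- Section 8.2, adverse event ground: it presupposes that the event has caused lens wear to stop.
- Section 8.2, infiltrative events: a clear stop.
- Section 8.2, loss of eligibility: reaches any Grade 3 finding if criterion 6 of section 3.3 is read as a continuing condition. The example given is pregnancy.
- Section 13.1: names Grade 3 corneal findings. The list is open-ended but does not name Grade 3 conjunctival injection or tarsal abnormalities, which criterion 6 does.
- Section 13.3: leaves continuation after an adverse event to the investigator's clinical judgment.
- Section 8.2, discontinuation tasks: finish the current visit, do the Final Evaluation, collect the used lenses. The steps still open after 2.11 include 2.13.

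The stop is therefore clearest for corneal findings and infiltrative events. For other Grade 3 findings it has to be inferred.

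**3. How many eyes**

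Inputs from section 14.2: no Grade 3 or higher finding in the four historical studies; planning incidence 0.5%, unit not stated; 120 completers, so 240 eyes; correlation 0.50 within subject and period. Four scheduled follow-up examinations (Visits 2 to 5) come from section 7.1.

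Expected eyes at Visit 2, under three readings of the rate:

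- per eye over the study, spread evenly over four examinations: 240 × 0.005 / 4 = 0.3
- per eye and period, split evenly over Visits 2 and 3: 240 × 0.005 / 2 = 0.6
- per eye and visit: 240 × 0.005 = 1.2

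If every event in the first two readings fell at Visit 2, each would also give 1.2. With 130 enrolled (260 eyes) the three figures are 0.325, 0.65 and 1.3.

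Expected subjects, taking 0.50 as the between-eye correlation (an assumption): P(at least one eye) = 2p − [p² + 0.5p(1 − p)].

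- p = 0.00125: 0.00187 × 120 = 0.22
- p = 0.0025: 0.00375 × 120 = 0.45
- p = 0.005: 0.00749 × 120 = 0.90 (0.97 with 130)

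These counts include corneal and infiltrative findings, so they overstate the number of eyes for which the stop must be inferred. The documents give no split by type of finding.

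**4. Effect on the endpoint**

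The finding is graded at 2.11, before any reinsertion. The biomicroscopy endpoint covers all follow-up visits, so the eye is already counted.

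**The case against.** The strongest reply is that no competent investigator would reinsert. The 2.11 note comes before 2.13, calls the subject ineligible, requires adverse event follow-up and puts the site in contact with the monitors immediately. Section 13.4 adds sponsor notice within 24 hours for serious or significant events, and section 13.2 brings in the medical monitor. Withdrawal under 8.2 is mandatory once a ground is met, and worn lenses are then collected. Even a site that read finishing the visit to include 2.13 would hand the lenses over at the end, so exposure on that path is the rest of the visit. In addition, the study flowchart and the content of the biomicroscopy procedure are not visible in the public document and may add handling instructions.

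Most of this stands, and it limits the point. A reader might infer that the protocol permits re-exposure, or that Visit 2 has no rule for Grade 3 findings. The documents support neither. Termination once the event has resolved sets the time of study exit; it does not say that wear continues until then.

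What does not fall away is the wording. An explicit order to reinsert conflicts with a stop that must be assembled from other sections, and for non-corneal Grade 3 findings no section names that stop.

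**Conclusion.** The point holds as a minor defect in a safety instruction: the Visit 2 table orders reinsertion unconditionally, and its grade rule gates the wrong event. The full 6-8 days of further wear require a site both to follow 2.13 and not to apply 8.2.

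The size is small: 0.3 to 1.2 eyes, or about 0.2 to 0.9 subjects, as an upper bound on those who rely on inference, and possibly none given the historical record. The range rests on the unstated unit of the 0.5% rate, on how findings spread over visits, and on the assumed between-eye correlation. The conclusion about the wording rests on none of these, only on the procedures visible in the public document.

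Two further inferences should be resisted. The primary safety comparison is not distorted, since no endpoint count changes. Nor does the mislabelled period at 4.12 let an affected subject go on into Period 3: the note there still ends in adverse event follow-up and termination, so it is a clerical slip.

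**What to change.** - Steps 2.10 and 2.13: reinsert only if all 2.11 findings are Grade 2 or less in both eyes. Otherwise stop study lens wear at once, report and follow as an adverse event, and discontinue under section 8.2.
- Step 2.11 note: make Grade 2 or less a condition for continued lens wear in Period 1.
- Step 2.14: apply only after reinsertion.
- Step 4.12: correct the label to Period 3.

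The cost is wording in four Visit 2 steps and one label at Visit 4. No visit, procedure, data item or analysis is added.

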7.3. Unscheduled Visits

If, during the investigation, a subject requires an unscheduled visit to the clinical site, the following information will be collected at a minimum:

- Chief complaint prompting the visit. If the reason is an adverse event, the applicable eCRF for the adverse event must be completed and subject record completed as appropriate
- Date and time of the visit and all procedures completed at the unscheduled visit
- Review of adverse event and concomitant medications
- Documentation of any test article dispensed or collected from the subject, if applicable
- Slit lamp findings (using the Slit Lamp Classification Scale)

If the Investigator withdraws a subject from the study, the final study visit case report forms must be completed indicating the reason(s) why the subject was withdrawn. The subject record must be completed documenting the date and primary reason for withdrawal and the study CRA notified.

Any ocular and non-ocular Adverse Events that are ongoing at the time of the study visit will be followed by the Investigator, within licensure, until they have resolved, returned to pre-treatment status, stabilized, or been satisfactorily explained. If further treatment i.e., beyond licensure is required, the subject will be referred to the appropriate health care provider.

The following information will be collected during an unscheduled visit.

Step	Procedure	Details	
U.1	Chief Complaints	Record the subject's chief complaints for reasons for the unscheduled visit	
U.2	Change of Medical History and Concomitant Medications	Questions regarding the change of subjects' medical history and concomitant medications.	
U.3	Entrance VA	Record the entrance distance visual acuity (OD, OS and OU) to the nearest letter.	
U.4	Subjective Sphero-cylindrical Refraction	The investigator will complete a subjective refraction (sphere and cylinder) and record the resultant distance visual acuity OD, OS, and OU to the nearest letter.	
U.5	Slit Lamp Biomicroscopy	FDA Slit Lamp Classification Scale will be used to grade the findings. If no slit lamp finding is noted on the EDC form it is considered as a zero "0" Grade for all observations listed. After the slit lamp examination, at the discretion of the Investigator, rinse the subject's eyes thoroughly with preservative-free saline.	
U.6	Dispensing (if applicable)	Additional lenses may be dispensed if one is lost or torn during the wearing period.	
U.7	Exit Visual Acuity	Record the subject's exit distance visual acuity (OD, OS and OU) to the nearest letter.	

